5.5 Treatment discontinuation

Patients may discontinue the treatment part of the study for any of the following reasons:

- Evidence of tumor progression by radiological assessment as measured by PCWG3 criteria
- Unacceptable toxicity
- Patient non-compliance or voluntary withdrawal
- Required use of a prohibited treatment
- Evidence that the patient is no longer clinically benefiting
- At the sponsor's or investigator's discretion

Patients that discontinue treatment due to unacceptable toxicity should return to the clinic for the End of Treatment visit. Participants who discontinue ¹⁷⁷Lu-PSMA-617 due to unacceptable toxicity may continue to receive best supportive/best standard of care alone during the treatment part of the study until they discontinue the treatment part of the study and enter long-term follow-up.

Before final analysis of alternate primary endpoint OS:

If a patient discontinues the treatment part of the study for any reason other than radiographic progression, they will be asked for permission to continue collecting radiographic images (bone scans and CT scans and/or MRIs) for the purpose of continuing to assess rPFS, unless they specifically withdraw consent from continued participation in the study.

After final analysis of alternate primary endpoint OS:

If a patient discontinues the treatment part of the study for any reason other than radiographic progression, no additional scanning will be required.

6. STUDY ASSESSMENTS AND PROCEDURES

6.1 Screening procedures and baseline assessments

Screening procedures and baseline assessments will be performed within 4 weeks of randomization except for baseline imaging. Any procedure or assessment done within this time frame may be accepted as the baseline procedure or assessment. Baseline medical imaging (CT with contrast/ MRI, and bone scan) is to be performed within 28 days of start of treatment. Any

medical imaging done within this time frame may be accepted as the baseline imaging. The screening procedures are detailed in Table 2.

Table 2 Screening procedures and baseline assessments

Screening Procedure or Baseline Assessment	Notes
Informed consent	As per local/central IRB/IEC/REB timing requirements but prior to the performance of any study specific procedures.
Inclusion/exclusion criteria	Refer to Section 4.1 and Section 4.2 for additional details.
Medical history	Collect medical history, including the following details about prior prostate cancer treatment(s): 
 • Date of initial diagnosis • Approximate start and stop date of each therapy • Date and type of progression (e.g. PSA, radiological, bone, or no clinical benefit) • Site of progression (new lesions, existing lesions, or both) when available
Prior/concomitant medication review	
Full physical examination	Should be performed by a qualified medical practitioner.
Height	
Weight	
ECOG performance score	Refer to Appendix 4 for the ECOG performance score scale.
Vital signs	Includes: blood pressure, pulse, and respiratory rate
CT with contrast/MRI	CT with contrast /MRI tumor assessments should include evaluations of the chest, abdomen, and pelvis using the RECIST v1.1 criteria with caveats outlined in the PCWG3 recommendations The radiological technique used for measurement of the baseline images should also be the radiological technique used for each reassessment.
^{99m} Tc diphosphonate bone scan	Baseline and follow up radiological disease assessments must include bone scans performed with technetium-99m labeled diphosphonates as per the local standard of care for patients with prostate cancer. Use the PCCTC bone scan assessment tool or equivalent to document lesions (included in Appendix 11).
Histology	Pathology report of the most recent biopsy required at enrollment.
Disease pattern	Bone, visceral, soft tissue, and lymph nodes
12-lead ECG	
Hematology	Refer to Section 6.3.1 for list of tests
Chemistry	Refer to Section 6.3.1 for list of tests
Urinalysis, macroscopic (microscopic when indicated)	Refer to Section 6.3.1 for list of tests

Table 2 Screening procedures and baseline assessments

Screening Procedure or Baseline Assessment	Notes
Serum/plasma testosterone	
PSA	Includes PSA results and dates of 2 previous measurements. Prior measurements are needed to assess PSA velocity/doubling time.
BPI-SF, EQ-5D-5L and FACT-P	Baseline pain score assessment (BPI-SF) and HRQoL (EQ-5D-5L, FACT-P) assessments. HRQoL assessments may be either self-completed by the subject or administered via face-to-face interview and completed by a caretaker/clinician.
Best supportive/best standard of care determination	To be decided prior to randomization, as part of screening.
PSMA PET/CT scan	To be done once all other eligibility requirements are confirmed. The metastatic lesion requirement may be confirmed at the same time as the baseline ⁶⁸ Ga-PSMA-11 PET/CT ^a scan. Baseline ⁶⁸ Ga-PSMA-11 PET/CT ^a scan must be done within 4 weeks (+ 2 weeks) of start of treatment but not within the 6 days prior to start of treatment. Study eligibility based on PSMA positivity will be determined by central readers.
Screening registration	Initial screening registration should take place after the patient has signed the Informed Consent Form. It should be completed once all screening assessments have been completed and results confirmed except for metastatic lesion requirement and PSMA positivity.
Study enrollment	Study enrollment should take place after screening registration is completed and once the metastatic lesion requirement is confirmed by the site and PSMA positivity has been confirmed by the central readers. Patients randomized to the investigational arm are to begin dosing with ¹⁷⁷ Lu-PSMA-617 within 28 days after randomization.

^a For background and additional details on ⁶⁸Ga-PSMA-11, refer to the ⁶⁸Ga-PSMA-11 Investigator's Brochure.

BPI-SF = Brief Pain Inventory – Short Form; CT = computed tomography; ECG = electrocardiography; ECOG = Eastern Cooperative Oncology Group; EQ-5D-5L = European Quality of Life (EuroQol) – 5 Domain 5 Level scale; FACT-P = Functional Assessment of Cancer Therapy – Prostate; HRQoL = Health-related quality of life; IEC = Independent Ethics Committee; IRB = Institutional Review Board; MRI = magnetic resonance imaging; PCCTC = Prostate Cancer Clinical Trials Consortium; PET = positron emission tomography; PSA = prostate-specific antigen; PSMA = prostate-specific membrane antigen; REB = Research Ethics Board; RECIST = Response Evaluation Criteria in Solid Tumors;

6.2 Efficacy assessments

For the timing of efficacy assessments, refer to the schedule of assessments provided in Appendix 1.

6.2.1 Radiographic imaging for tumor assessments

Radiologic assessment should follow PCWG3 guidelines. Periodic radiographic imaging will include both:

- CT with contrast/MRI imaging
- Bone scans with technetium-99m labeled diphosphonates

CT with contrast/MRI tumor assessments should include evaluations of the chest, abdomen, and pelvis.

Disease progression by bone scan will be defined as at least 2 new bone lesions at the first post-treatment scan, with at least two additional lesions on the next (confirmatory) scan (2+2 PCWG3 criteria, Scher et al 2016). For scans after the first post-treatment scan, at least two new lesions relative to the first post-treatment scan confirmed on a subsequent scan (2+2 PCWG3 criteria). If the second scan confirms the metastases, then the date of progression is the date of the scan when the first 2 new metastases were documented.

6.2.2 Additional Imaging Analyses

The baseline eligibility ⁶⁸Ga-PSMA-11 scan data will be used for additional exploratory analyses. The ⁶⁸Ga-PSMA-11 PET/CT and corresponding diagnostic CT/MRI scans will be used in a retrospective Independent Review assessing inter-reviewer variability. The Independent Review will serve to evaluate the reading procedure for ⁶⁸Ga-PSMA-11 PET/CT scans by assessing the variability and reproducibility of visual assessment. Visual assessment will be independently performed by three reviewers on ⁶⁸Ga-PSMA-11 PET/CT scans and corresponding diagnostic CT/MRI scans.

In addition, Quantitative Analysis will also be performed to assess tumor burden and tumor characteristics on ⁶⁸Ga-PSMA-11 PET/CT scans at the time of enrolment. The association of these baseline data with rPFS, OS, and other efficacy endpoints will be assessed in exploratory analyses.

An imaging charter will provide a detailed and expanded description of the planned analyses.

6.2.3 RECIST criteria

The responses of soft tissue, lymph node, and visceral lesions to treatment will be characterized using the RECIST v1.1 criteria with caveats outlined in the PCWG3 recommendations (see Appendix 6 and Appendix 7).

6.2.4 Symptomatic skeletal events

The time to the first SSE will measure the time to the first new symptomatic pathological bone fracture, spinal cord compression, tumor-related orthopedic surgical intervention, requirement for radiation therapy to relieve bone pain or death from any cause, whichever occurs first.

6.2.5 Pain score

Pain will be assessed using the Brief Pain Inventory – Short Form (BPI-SF).

The Brief Pain Inventory- Short Form will be used as part of this study to assess the severity of pain and the impact of pain on daily functions. Full details regarding the BPI-SF, its validation and clinical application are available in the Brief Pain Inventory User Guide (Cleeland 2009).

A copy of the BPI-SF questionnaire is provided in Appendix 8.

6.2.6 Health-related quality of life

The ECOG Performance Status scale will be used to assess patients' ability to perform daily living tasks and their range of basic physical ability. A copy of the ECOG scale is provided in Appendix 4.

The EQ-5D-5L questionnaire will also be administered as a part of this study to assess HRQoL. EQ-5D is an international, validated, standardized, generic questionnaire for describing and valuing HRQoL (Rabin 2001). EQ-5D was developed by the EuroQol Group in order to provide a simple, generic measure of health for clinical and economic appraisal (EuroQoL Group 1990). This instrument generates a preference-based health-state utility score (EQ-5D utility index) and an overall health-state score based on a visual analogue scale (EQ-5D VAS).

EQ-5D is designed for self-completion by respondents and is ideally suited for use in clinics and face-to-face interviews. It is cognitively undemanding, taking only a few minutes to complete. Instructions to respondents are included in the questionnaire. The most recent version of EQ-5D is the EQ-5D-5L, which was developed to improve the instrument's sensitivity and to reduce ceiling effects. The number of dimensions (mobility, self-care, usual activities, pain/discomfort, anxiety/depression) has not changed, however the new version includes five levels of severity in each of the existing dimensions in place of three (EuroQoL Group 2015). Full details regarding the EQ-5D-5L questionnaire, including references, are available at the EQ-5D website: <https://euroqol.org/eq-5d-instruments/eq-5d-5l-about>.

A copy of the EQ-5D-5L questionnaire is provided in Appendix 9

The FACT-P questionnaire will also be administered as part of this study to specifically assess the HRQoL of prostate cancer patients. The FACT-P is made up of 2 parts: the FACT-G (general) questionnaire with 27 questions, and the Prostate Cancer Subscale (PCS) with an additional 12 questions. The FACT-G (Functional Assessment of Cancer Therapy – General) questionnaire is one of the most widely used HRQoL instruments and measures HRQoL in four different domains: Physical well-being, Functional well-being, Emotional well-being, and Social/Family well-being (Cella et al 1993). The PCS is designed specifically to measure prostate cancer-specific quality of life. Each item in both the FACT-G and PCS is rated on a 0 to 4 Likert-type scale, and then combined to produce subscale scores for each domain, as well as global quality of life score with higher scores representing better QoL. The FACT system has a number of advantages as a method of measuring QoL:

- Questionnaires have been developed to reflect patients' concerns
- Measurements are reliable, reproducible, and have been validated in numerous studies (Cella et al 1993, Esper et al 1997)
- Available in over 45 different languages
- Designed for patient self-administration, but can also be administered by interview format (Webster et al 2003)

Full details regarding the FACT-P questionnaire, including references, are available at the FACIT website: <http://www.facit.org/FACITOrg/Questionnaires>.

A copy of the questionnaire (FACT-P version 4) is provided in Appendix 10.

HRQoL will be periodically assessed at baseline, prior to administration of each cycle of ¹⁷⁷Lu-PSMA-617, and through the End of Treatment visit.

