Investigational product:	
Patients randomized to receive the investigational product will receive 7.4 GBq ($\pm 10\%$) ^{177}Lu-PSMA-617 intravenously every 6 weeks (± 1 week) for a maximum of 6 cycles. After 4 cycles, patients will be assessed for (1) evidence of response, (2) residual disease, and (3) tolerance to ^{177}Lu-PSMA-617. If the patient meets the criteria above and agrees to continue with additional treatment of ^{177}Lu-PSMA-617 radioligand therapy, the investigator may administer 2 additional cycles. A maximum of 6 cycles of radioligand therapy is allowed. After the last cycle of ^{177}Lu-PSMA-617, patients can continue best supportive/best standard of care alone. If the patient does not meet all of the criteria or does not agree to additional ^{177}Lu-PSMA-617 treatment, then no additional doses of ^{177}Lu-PSMA-617 will be administered after Cycle 4. These patients can continue on best supportive/best standard of care alone after Cycle 4.

Assessment schedule:	
Radiographic imaging will be done every 8 weeks (± 4 days) during the first 24 weeks of treatment and every 12 weeks (± 4 days) thereafter, regardless of treatment delays, through the End of Treatment visit.
 
The previous 2 PSA values will be noted before randomization. Serum/plasma testosterone and PSA levels will be measured up to 3 days prior to Day 1 of each cycle. Hematology and chemistry will be done weekly during Cycle 1 (up to 3 days prior to each time point) and up to 3 days prior to Days 1, 15, and 29 in Cycles 2 to 6 (i.e. every two weeks). After Cycle 6, hematology and chemistry will be done every 12 weeks (± 4 days) until the patient starts long-term follow-up.
 
Patients will complete the BPI-SF, EQ-5D-5L and FACT-P questionnaires about their pain level and HRQoL during screening and prior to treatment on Day 1 of

	
each cycle and through the End of Treatment visit. Patients will be monitored throughout the study for SSEs.
 
After the final analysis of OS, patients in the active part of the study will have an end of treatment (EOT) visit and move into long-term follow-up. Long-term follow-up will be extended on this study until a long-term safety follow-up study is available in the respective country (estimated in 2nd quarter of 2023).

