Hematological toxicity (except lymphocytopenia that responds to medical intervention)	Grade 3 or Grade 4	Hold ^{177}Lu -PSMA-617 administration until improvement to Grade 1 or baseline. Reduce ^{177}Lu -PSMA-617 dose by 20% on the next cycle
Serum/plasma creatinine increased $\geq 40\%$ from baseline AND calculated creatinine clearance decreased $>40\%$ from baseline		Reduce ^{177}Lu -PSMA-617 dose by 20% on the next cycle

Table 1 Toxicity management and dose modification recommendations

Event	Grade	Management recommendations
Salivary gland toxicity	≥ Grade 2	Reduce ¹⁷⁷ Lu-PSMA-617 dose by 20% on the next cycle
Non-hematological, clinically significant toxicity not otherwise stated	≥ Grade 2	Hold ¹⁷⁷ Lu-PSMA-617 administration until resolved to Grade 1 or baseline
Electrolyte or metabolic abnormalities that are correctable within a 48 hr period without sequela	≥ Grade 2	Hold ¹⁷⁷ Lu-PSMA-617 administration until resolved to Grade 1 or baseline
Gastrointestinal toxicity (not amenable to medical intervention)	≥ Grade 3	Hold ¹⁷⁷ Lu-PSMA-617 administration until resolved to Grade 2 or baseline Reduce ¹⁷⁷ Lu-PSMA-617 dose by 20% on the next cycle
Fatigue	≥ Grade 3	Hold ¹⁷⁷ Lu-PSMA-617 administration until resolved to Grade 2 or baseline
Pain	≥ Grade 3	Hold ¹⁷⁷ Lu-PSMA-617 administration until resolved to Grade 2 or baseline
Spinal cord compression		Hold ¹⁷⁷ Lu-PSMA-617 administration until the compression has been adequately treated and hematological parameters have returned to Grade 1 or baseline and ECOG performance status has returned to baseline at the time the next cycle administration is due
Fracture in weight bearing bones		Hold ¹⁷⁷ Lu-PSMA-617 administration until fracture is adequately stabilized/treated and hematological parameters have returned to Grade 1 or baseline and ECOG performance status has returned to baseline at the time the next cycle administration is due
AST or ALT >5 × ULN in the absence of liver metastases		Discontinue ¹⁷⁷ Lu-PSMA-617
Renal toxicity	≥ Grade 3	Discontinue ¹⁷⁷ Lu-PSMA-617
Any serious AE that requires drug discontinuation or treatment delay of >4 weeks		Discontinue ¹⁷⁷ Lu-PSMA-617
Any unacceptable toxicity		Discontinue ¹⁷⁷ Lu-PSMA-617

Note: Hematologic parameters (i.e., CBC with differential analysis) will be monitored every week in Cycle 1 only. Cycles 2 to 6, it will be monitored every 2 weeks. After Cycle 6, it will be monitored every 12 weeks.

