Appendix 1 Schedules of Assessments

Table 3 Schedule of assessments: ^{177}Lu -PSMA-617 plus best supportive/best standard of care arm (Cycle 1)

Study Period:	Cycle 1					
	Week 1	Week 2	Week 3	Week 4	Week 5	Week 6
Cycle Week:	Day 1	Day 8	Day 15	Day 22	Day 29	Day 36
Concomitant medication review	X-----					X
AE monitoring ^a	X-----					X
Weight	X ^b					
ECOG	X ^b					
Directed physical exam	X ^b					
Vital signs ^c	X ^b					
EQ-5D-5L	X ^{d,f}					
FACT-P	X ^{d,f}					
BPI-SF	X ^{d,f}					
Administer ^{177}Lu -PSMA-617	X					
Best supportive/best standard of care	As per physician's orders					
Hematology ^e	X ^b	X ^b	X ^b	X ^b	X ^b	X ^b
Chemistry ^e	X ^b	X ^b	X ^b	X ^b	X ^b	X ^b
Serum/plasma testosterone	X ^b					
PSA	X ^b					
Radiographic imaging (CT with contrast/MRI and bone scan)	Every 8 weeks (\pm 4 days) after first dose of ^{177}Lu -PSMA-617 for the first 24 weeks (independent of dose delays), then every 12 weeks (\pm 4 days)					

^a Adverse event monitoring will commence at time of consent.

^b Can be done up to 3 days prior to Day 1. For hematology and chemistry: up to 3 days prior to Days 1, 8, 15, 22, 29, and 36.

^c Blood pressure, pulse and respiratory rate will be assessed at required physical exams (up to 3 days of Day 1) and at 15(+/-5) minutes before, 30 (+/-5) minutes post, and 60 (+/-5) minutes post ^{177}Lu -PSMA-617 administration.

^d To be completed prior to drug administration on Day 1. Can be completed up to 3 days prior to Day 1.

^e Hematology and chemistry to be done every week for Cycle 1 only.

^f HRQoL and pain assessments may be self-completed by subject or administered in interview format and completed by a caretaker, clinician or site research team member.

AE = adverse event; BPI-SF Brief Pain Inventory – Short Form; CT = computed tomography; ECOG = Eastern Cooperative Oncology Group; EQ-5D-5L = European Quality of Life (EuroQol) – 5 Domain 5 Level scale; FACT-P = Functional Assessment of Cancer Therapy – Prostate; MRI = magnetic resonance imaging; PSA = prostate-specific antigen

Table 4 Schedule of assessments: ^{177}Lu -PSMA-617 plus best supportive/best standard of care arm (Cycles 2 to LTFU)

Study Period:	Cycles 2-6*						After Cycle 6**	End of Treatment ^g	Long-term follow-up (Before final analysis of alternate primary endpoint OS)	Long-term follow-up Extension (after final analysis of primary alternate endpoint OS)

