If the patient meets the criteria above, and agrees to continue with additional treatment of ¹⁷⁷Lu-PSMA-617, the investigator may administer a further 2 cycles. A maximum of 6 cycles of radioligand therapy is allowed. If the patient does not meet all of the criteria or does not agree to additional ¹⁷⁷Lu-PSMA-617 treatment, then no additional doses of ¹⁷⁷Lu-PSMA-617 will be administered after Cycle 4. After the last cycle of ¹⁷⁷Lu-PSMA-617, patients can continue best supportive/best standard of care alone.

** Cycles 2-6 are 6 weeks long. Cycle 7 Day 1 should occur after 6 full weeks from C6D1 (Day 43 of Cycle 6). Starting with Cycle 7, all cycles are 12 weeks long. The stipulated windows apply to C7D1 required procedures and for all cycles afterwards.

^a Phone evaluations are allowed, but are not required for visits after Day 1 of each cycle.

^b Adverse event monitoring will commence at time of consent.

^c Can be done up to 3 days prior to Day 1. For hematology and chemistry: up to 3 days prior to Days 1, 15, and 29.

^d Blood pressure, pulse and respiratory rate will be assessed at required physical exams (up to 3 days of Day 1) and at 15(+/-5) minutes before, 30(+/-5) minutes post, and 60(+/-5) minutes post ¹⁷⁷Lu-PSMA-617 administration.

^e To be completed prior to drug administration (if applicable) on Day 1. Can be completed up to 3 days prior to Day 1.

^f For Cycles 2 to 6: Hematology and chemistry to be done at Days 1, 15, and 29 (every 2 weeks). After Cycle 6, to be done on Cycle 7 Day 1 and then every 12 weeks (\pm 4 days).

^g To be done once a patient is to enter the long-term follow-up part of the study. To occur approximately 30 days from the last dose of ¹⁷⁷Lu-PSMA-617 or last dose or intervention of best supportive/best standard of care end of treatment decision, but before the initiation of subsequent anticancer treatment, outside of what is allowed on study

^h HRQoL and pain assessments may be self-completed by subject or administered in interview format and completed by a caretaker, clinician or site research team member.

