5.1.2 Visit Windows

For data collected at multiple time points, the scheduled collection date/time will be used to summarize the data, unless otherwise indicated. Visits are scheduled from time of previous cycle's Day 1.

Scan assessments are scheduled from the reference date (date of first dose). Scan dates are not associated with a visit number. Dates are used for analyses and patient listings.

Unscheduled assessments will not be taken into account in summary variable calculations, except for baseline assessments and unscheduled RECIST, bone scan, PSA and HRQoL evaluations for evaluating efficacy (Section 8). All measurements will be presented in the listings.

Unless otherwise indicated, if more than one measurement (a lab result for example) exists for a patient on a particular time point/visit, the last value obtained at that time point/visit will be used when summarizing the data.

Refer to protocol section 6.1 and protocol Appendix 1 for schedules of study assessments during each study period.

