Change from baseline in utility score will also be analyzed using general linear models for repeated measures. Baseline value (as a continuous variable), treatment arm, time (as visit number), treatment by time interaction, baseline by time interactions, and randomization stratification factors as main effects will be the fixed factors. A general (unstructured) variance-covariance matrix for the repeated measures for a single patient will be used. In case of problems with fitting the model, as an alternative, a heterogeneous Toeplitz and AR(1) structures will be considered to reduce the number of the parameters of the model. The differences in least square means between the treatment arms and corresponding 95% confidence interval at selected time points will be presented.

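### HRQoL and pain forms follow the 177Lu dosing day, so a held dose postpones them in the investigational arm only, and the SAP then compares the arms by visit number

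*Protocol*

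**What the plan says.** - **When the forms are due.** Protocol 6.2.6 ties HRQoL assessment to each administration ("HRQoL will be periodically assessed at baseline, prior to administration of each cycle of" 177Lu-PSMA-617). The synopsis has patients report pain and "HRQoL during screening and prior to treatment on Day 1 of" each cycle. Table 3 footnote d reads "To be completed prior to drug administration on Day 1. Can be completed up to 3 days prior to Day 1"; Table 4 footnote e reads "To be completed prior to drug administration (if applicable) on Day 1. Can be completed up to 3 days prior to Day 1". SAP 8.2.3.3 names cycle Day 1 and the EOT visit as the collection times.
- **What moves Day 1.** Protocol Table 1 holds the dose for many toxicities. For other clinically significant non-hematological toxicity of Grade 2 or more, the hold is on "administration until resolved to Grade 1 or baseline". Under 5.1.4, 177Lu is discontinued if a toxicity delay lasts more than 4 weeks. SAP 5.1.2 adds: "Visits are scheduled from time of previous" cycle's Day 1, so a delay carries forward.
- **Control.** Table 6 gives 6-week cycles through Cycle 6 and 12-week cycles after that. These nominal lengths match the investigational arm, but control has no 177Lu dose to hold.
- **Imaging.** The synopsis requires scans every 8 weeks for the first 24 weeks and every 12 weeks "thereafter, regardless of treatment delays, through the End of Treatment visit". Tables 3 to 6 repeat that scans are independent of dose delays. The questionnaires carry no such wording.
- **Analysis.** The EQ-5D-5L utility model has fixed factors that include "treatment arm, time (as visit number), treatment by time interaction" (SAP 8.2.3.3.1). FACT-P and BPI-SF use the same model. The SAP defines no calendar windows for HRQoL and no sensitivity analysis for delayed cycles.

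**The concern.** In one arm the measurement date depends on the outcome being measured. A patient whose dose is held for toxicity is next required to answer once the hold has ended; a control patient is due to answer on the planned date whatever his symptoms. Three things follow in held cycles:

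1. Symptoms present on the planned date may go unrecorded.
2. Worsening is detected later, which favours 177Lu in the time-to-worsening analyses.
3. The same visit number stands for different times since randomization in the two arms.

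The trial is open-label, HRQoL and pain are stated secondary objectives, and EQ-5D responses supply the quality adjustment for QALYs (protocol 6.2.7). The protocol already guards against this dependence for scans.

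**Working it through.** The documents state no power, effect size or hold rate for HRQoL or pain, so there is no planned figure to reproduce.

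**Inputs from the documents.** Nominal cycle 6 weeks through Cycle 6; longest toxicity delay 4 weeks; five doses that can be held for 177Lu toxicity (Cycles 2 to 6); recall of 7 days for FACT-P, mostly 24 hours for BPI-SF, and today for EQ-5D-5L.

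**Step 1: dates.** Day 1 of cycle k+1 falls at 6k weeks plus the sum of earlier holds.

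| Case | Day 1 of Cycles 1 to 7 (weeks) |
|---|---|
| Control | 0, 6, 12, 18, 24, 30, 36 |
| One 4-week hold before Cycle 3 | 0, 6, 16, 22, 28, 34, 40 |
| 4 extra weeks in every cycle (extreme) | 0, 10, 20, 30, 40, 50, 60 |

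In the extreme case Cycle 6 Day 1 is at week 50 against week 30, and 4 forms against 7 are due by week 36.

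**Step 2: average drift.** If a fraction p of doses is held for d weeks, the mean shift of Cycle 6 Day 1 is 5 × p × d. With p from 5% to 40% and d from 2 to 4 weeks (assumed), this runs from 5 × 0.05 × 2 = 0.5 weeks to 5 × 0.40 × 4 = 8 weeks.

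**Step 3: later detection alone.** Give both arms the same exponential time to lasting worsening, detected at the next Day 1, so the true ratio is 1.

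- Medians of 10, 17 and 26 weeks, holds of 2 or 4 weeks in 5, 10, 20 or 40% of cycles, 52 weeks of follow-up: the simulated event-rate ratio is 0.945 to 1.006. The lowest value is for a median of 10 weeks with 4-week holds in 40% of cycles.
- Median 4 months, holds of 1 to 4 weeks in 10, 20 or 30% of cycles, six planned visits, 20,000 patients per arm: the Cox hazard ratio is 0.958, 0.941 and 0.933. A repeat run gave about 0.97, 0.95 and 0.93.

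Together: about 0.93 to 1.00. Both simulations omit clinical progression and death, which also count as worsening events and are not tied to Day 1, so they would dilute the effect.

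**Step 4: missed symptoms.** A symptom lasting 7 to 9 weeks after a dose is present at week 6 and gone at week 10. With the recall periods above, a form completed at week 10 does not recover it. How often this happens depends on a rate that the documents do not give.

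**Step 5: visit number as time.** After one 4-week hold before Cycle 3, the Cycle 3 visit compares week 16 in that patient with week 12 in control. Four more weeks of disease would tend to count against 177Lu; recovery during the hold would count for it.

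**The case against.** The strongest reply concerns reach and size, and much of it stands.

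- **Only held cycles are affected.** Table 1 gives recommendations, delay or reduction is at the investigator's discretion, and 5.1.4 asks for every effort to keep the 6-week cycle. Salivary gland and creatinine toxicity carry no hold. Fatigue, pain and gastrointestinal holds start at Grade 3 and end at Grade 2 or baseline, so such a patient may still be symptomatic when asked. Many other holds are for cytopenias, and 5.1.4 calls symptomatic hematologic toxicity uncommon.
- **Some episodes may be captured.** A form can be completed in the 3 days before a Day 1 that is then held, and SAP 5.1.2 keeps unscheduled HRQoL forms for efficacy. Patients who stop for unacceptable toxicity should have an EOT visit, which includes all three questionnaires. But no form is required on the planned date, and if two forms fall under one visit, SAP 5.1.2 generally summarizes the last.
- **A fixed grid is not complete either.** Protocol 5.1.4 places the most common adverse events in the first few days of treatment, and a 6-week grid misses those too.
- **The endpoints are nominal.** They carry no alpha control, and the SAP calls the HRQoL p-values nominal and descriptive.

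None of this removes the arm-dependent measurement date or supplies a time scale shared by the arms.

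**Conclusion.** The point holds for cycles in which a dose is held. It is a modest, inexpensively corrected weakness in additional secondary HRQoL and pain endpoints and in the EQ-5D input to QALYs. rPFS, OS and the key secondary endpoints are untouched. Later asking alone moves the time-to-worsening hazard ratio to about 0.93 to 1.00 from a true 1, under assumed holds in 5 to 40% of cycles.

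Two stronger readings are not supported. A reader might infer that the investigational arm is generally asked only after recovery; Table 1 does not bear that out, for the reasons above. A reader might also infer a large hidden harm. If a fraction q of cycles has a held, unrecorded toxicity that meets the worsening threshold, and disease-related worsening per visit is 15% on 177Lu and 21.3% in control, the true hazard ratio is ln[0.85 × (1 − q)] / ln(0.787). This is 0.70 at q = 0.5%, 0.89 at 5% and 1.12 at 10%, against a reported 0.68 in every case. The answer is set by q, and neither q nor the per-visit rates are in the documents, so no such figure should be quoted. Nor does every error favour 177Lu: later detection does, but the visit-number comparison can go either way.

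**What to change.** 1. **Protocol 6.2.6 and Tables 3 to 6.** Make the three questionnaires due at fixed 6-week dates from Cycle 1 Day 1, and 12-weekly after the sixth interval, in both arms, independent of dose delays, as already written for imaging. Both arms would then be due at weeks 0, 6, 12, 18, 24, 30 and 36, with no shift between them. The cost is one sentence in the schedule tables and one extra electronic form per held dose.
2. **SAP 8.2.3.3.** Assign every dated form, including unscheduled ones, to a window by weeks since randomization. Use that window instead of visit number as the time factor in the repeated-measures models and by-visit plots, or at least as a sensitivity analysis. This can be done on forms already collected.
3. **Limitation to state.** Windows realign dates; they cannot recover forms never collected during holds. The table of delayed cycles with reasons already planned in SAP 9.1 would show how many cycles are exposed.

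Nothing here changes dosing or the hold rules.
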